Participants will be asked to give a baseline salivary sample (5ml over 5 minutes) and then asked to rinse with an unlabeled (blinded) antiseptic mouth rinse for 60 seconds according to the table below. The rinses and control will be similar in appearance visually, such that a double-blind can be maintained. The research assistant ([name]) will be the sole unblinded staff member who will perform randomization and communicate the subject's group assignment to blinded study staff, in advance of the visit based on the block randomization schedule. The unblinded staff member will set-up the rinses for the participants appointment minimizing the possibility of study staff being able to identify the blinded rinses. In the instance that [name] is unavailable, [name] or [name] will perform randomization and set-up the rinses. Blind will be strictly maintained except in the case of medical emergency requiring reveal of an individual's rinse identity. The product group key will be provided to the analyzing statistician at the conclusion of the clinical study.

mouth rinse*	Number of participants (sample size)	Group
26.9% ethanol plus essential oils	84	Experimental
0.1% Cetylpyridinium Chloride	84	Experimental
Sterile water	84	Control

**All mouth rinses are commercially available in the USA, routinely used in clinical settings, and will be used in an on-label manner.*

After the participant expectorates the mouth rinse, research staff will collect another salivary sample (T_0 , 2 mL over 5 minutes). During a 10 minute recuperation period, the study participants will answer demographics survey questions and questions regarding the taste, color, flavor and general acceptability of using the mouth rinse as part of routine dental and medical visits as well as in social settings. At 15 minutes post-rinse, the participant will be asked to provide an additional saliva sample (2 mL over 5 minutes), followed by another 10 minute recuperation period. This sequence will be repeated for at

the 30, 45 and 60-minute time points post rinse. At 60 minutes, the study participant will give their final salivary sample (2 mL over 5 min), and study participation will conclude.

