5. STUDY INTERVENTIONS

5.1 Interventions, Administration, and Duration

Patients who meet all inclusion criteria without any exclusions will be asked to give a baseline salivary sample of 5ml over 5 minutes. The patient will then be asked to rinse with an unlabeled/blinded antiseptic mouth rinse for 60 seconds. Once s/he expectorates the mouth rinse, a time 0, 2ml salivary sample will be collected over 5 minutes. Then the patient will have 10 minutes to recuperate, while answering survey questions about their demographics and regarding the taste, color, flavor and acceptability of using the mouth rinse as part of routine dental and medical visits. Intra-oral photographs of notable lesions may be taken to document oral manifestations of COVID-19. At 15 minutes post-rinse, the patient will be asked to provide an additional 2ml saliva samples over 5 minutes,

followed by another 10 minute break. This sequence repeats for the 30, 45 and 60 minute time points. At 60 minutes, the patient will give their last salivary sample, and study participation will conclude. Participants will be provided with a gift card for their participation.

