6.2.5 Completion/Final Evaluation

This study requires only one 70-90 minute, single visit appointment. After consenting and randomization, subjects will be asked to rinse with an unlabeled/blinded antiviral mouth rinse for 60 seconds and provide 5 mL of saliva prior to the rinse and 2 mL of saliva immediately post-rinse, 15 minutes post-rinse, 30 minutes post-rinse, 45 minutes post-

rinse, and 60 minutes post-rinse. Subjects will also be asked to complete a short survey about the rinsing experience.

Subjects may withdraw from the trial at any time at their own request, or they may be withdrawn at any time at the discretion of the Investigator or Sponsor for safety, behavioral or administrative reasons.

The Investigator may discontinue a subject if, in the opinion of the Investigator, the subject is no longer a suitable candidate for the study. Possible reasons for the discontinuation of a subject are including but not limited to: adverse event, protocol deviation, missed appointment, subject no longer meets the eligibility criteria.

Patients may be removed from the study due to an allergic reaction to a mouth rinse or due to failure or inability to comply with study procedures.

If a patient suffers from severe xerostomia/dry mouth, such that s/he cannot produce the baseline salivary sample volume or the immediate, 15 minute and 30 minute post-rinse saliva volumes, s/he will be removed from the study with a parking voucher, but without a gift card and will be replaced. If a patient suffers from dry mouth, such that s/he cannot produce salivary sample volumes needed for later time points (45 minutes or 60 minutes post-rinse) but s/he produced sufficient baseline, immediate, 15 minute and 30 minute post-rinse samples, s/he will still be compensated with a gift card and parking vouchers, and will remain in the study. Missing or deficient salivary samples will be noted in CDART. Severe xerostomia is an exclusion criteria during screening, yet we anticipate that some individuals may not know that they have severe xerostomia until they are participating in the study visit and then need to discontinue due to reduced salivary flow, as described.

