7.3 Adverse Events and Serious Adverse Events

An **adverse event (AE)** is generally defined as any unfavorable and unintended diagnosis, symptom, sign (including an abnormal laboratory finding), syndrome or disease which either occurs during the study, having been absent at baseline, or if present at baseline, appears to worsen. Adverse events are to be recorded regardless of their relationship to the study intervention.

A serious adverse event (SAE) is generally defined as any untoward medical occurrence that results in death, is life threatening, requires inpatient hospitalization or prolongation of existing hospitalization, results in persistent or significant disability/incapacity, or is a congenital anomaly.

The use of on-label, widely used mouth rinses (like Listerine) and collection of saliva carry minimal risk for participants, apart from the very rare, undiagnosed allergy, or the unlikely event that a participant slips or falls during the study, which would be managed through proper referral to the neighboring UNC hospital.

The investigator and team will meet weekly to review safety concerns, unanticipated problems or adverse events. All adverse events will be reported to the IRB and the committee overseeing the study within 30 days.

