8. INTERVENTION DISCONTINUATION

Subjects may withdraw from the trial at any time at their own request, or they may be withdrawn at any time at the discretion of the Investigator or Sponsor for safety, behavioral or administrative reasons.

The Investigator may discontinue a subject if, in the opinion of the Investigator, the subject is no longer a suitable candidate for the study. Possible reasons for the

discontinuation of a subject are including but not limited to: adverse event, protocol deviation, missed appointment, subject no longer meets the eligibility criteria.

Patients may be removed from the study due to an allergic reaction to a mouth rinse or due to failure or inability to comply with study procedures.

If a patient suffers from xerostomia/dry mouth, such that s/he cannot produce the baseline salivary sample volume or the immediate, 15 minute and 30 minute post-rinse saliva volumes, s/he will be removed from the study with a parking voucher, but without a gift card and will be replaced. If a patient suffers from dry mouth, such that s/he cannot produce salivary sample volumes needed for later time points (45 minutes or 60 minutes post-rinse) but s/he produced sufficient baseline, immediate, 15 minute and 30 minute post-rinse samples, s/he will still be compensated with a gift card and parking vouchers, and will remain in the study. Missing or deficient salivary samples will be noted in CDART.

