9. STATISTICAL CONSIDERATIONS

9.1 General Design Issues

A double-blinded, randomized controlled trial was chosen as the study design. It allows us to collect human based data on the effects of commercially available mouth rinses on salivary infectivity and viral load. A crossover study was not pursued because the repeated use of different mouth rinses is likely to confound the results. A 1-hour time-course was chosen to correspond with the average length of most dental procedures. Fifteen minute intervals were chosen to evaluate viral kinetics over time, and to see when infectivity rebounds post- mouth rinse.

Statistical Hypothesis

The central hypothesis of this study is that a 60 second antiseptic mouth rinse will effectively reduce viral infectivity (>50%) of SARS-CoV-2 for a minimum of 30 minutes duration.

The secondary hypothesis is that a 60 second mouth rinse will be well tolerated in a clinical care setting by a majority of patients and providers.

Sample Size Considerations

Based on our similar viral load studies evaluating mouth rinse efficacy against SARS-CoV-2 and other enveloped viruses, we used power calculations to estimate effect size and determine sample size as a function of length of mouth rinse time course.¹² With simultaneous comparisons, the sample size n=43 for each mouth rinse can detect the effect size in Cohen's $d = 0.8$, which is between medium and large, under 80% power and 0.016 type-I error rate by Bonferroni correction.¹² To account for 14% of patients having no virus in their saliva and 10% of patients producing insufficient saliva, we plan to enroll 55 participants per arm.

Statistical analysis of our deidentified data will be performed by [name], the statistician on this project.

Primary Outcomes

The analyses will compare viral RNA level (qRT-PCR) and viral infectivity levels between mouth rinse types and across the time course

Data generated from the qRT-PCR assays will be presented as mean standard deviation for normally distributed data and as median [Interquartile range] for non-normally distributed data. P values will be reported as two tailed. Between group comparisons will be performed using a Student's t test or Mann-Whitney U test. Normality will be assessed using the Kolmogorov-Smirnov test, and logistic regression will be performed with robust standard errors.

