10.3.3 Metrics

Every salivary sample will be collected in a conical tube with millimeter markings to monitor salivary volume. If insufficient saliva is collected, the study personnel collecting

the samples from participants will note insufficient volume in the CDART database for each applicable time point and will indicate in CDART if the subject must be withdrawn and replaced. If a patient is unable to generate sufficient saliva for the 0 min, 15 minutes or 30 minutes post-rinse time points, the subject will be removed from the study and this will be noted in CDART along with their insufficient samples. If a subject is unable to generate sufficient saliva for time points 45 or 60 minutes post-rinse, the patient will remain in the study but their insufficient samples will be noted in CDART.

For RT-PCR and viral infectivity assays, all salivary samples will be run in triplicate with standard experimental controls (negative and positive) and protocol quality checks performed by research technical personnel in the COVID core, [name], [name] and [name] laboratories.

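### Participants who run short of saliva within 30 minutes after the rinse are removed and replaced, with undiagnosed dry mouth as the only stated explanation and no count by arm, so a drying effect of a rinse could go unreported

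*Combined protocol and SAP*

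**What the plan says.** **Order of events.** Section 3 states: "Participants will be asked to give a baseline salivary sample (5ml over 5 minutes) and then asked to rinse". Section 5.1 gives the same "baseline salivary sample of 5ml over 5 minutes". After the rinse, at each later time point, section 3 asks the participant to "provide an additional saliva sample (2 mL over 5 minutes"; the immediate sample has the same volume and time.

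**Removal.** Sections 6.2.5 and 8 remove and replace anyone who cannot give the baseline volume or the 0, 15 and 30 minute volumes. Section 10.3.3 has a matching rule for anyone "unable to generate sufficient saliva for the 0 min, 15 minutes or 30 minutes post-rinse time points, the subject will be removed". People who fall short only at 45 or 60 minutes stay in.

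**Explanation.** Section 6.2.5 adds that "some individuals may not know that they have severe xerostomia until they are participating in the study visit". Section 8 repeats the rule without that sentence.

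**Recording.** Section 8 says: "Missing or deficient salivary samples will be noted in CDART". Section 10.3.3 has staff log insufficient volume for each time point, and whether the person must be withdrawn.

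**Safety and tolerability.** Section 7.3 defines an adverse event as an unfavourable, unintended finding "which either occurs during the study, having been absent at baseline, or if present at baseline, appears to worsen", recorded whatever its cause. Section 9.1 holds that "a 60 second mouth rinse will be well tolerated in a clinical care setting" by most patients and providers. Section 1.3 surveys all enrolled patients on taste, appearance, sensation and acceptability.

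**The concern.** A single rule covers two different situations. Someone who cannot give the baseline sample has not been exposed to anything, and undiagnosed dry mouth is a natural explanation. Someone who gives the baseline sample, rinses and then cannot give a smaller one has been randomised and exposed. For that person, a drying effect of the rinse is one of the possible causes. The plan offers only the pre-existing explanation, then takes the participant out and fills the place.

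The tolerability question is at stake. If one rinse reduces saliva flow, the people affected are the ones removed, and no planned summary would show that one arm lost more of them. The water arm goes through the same repeated sampling, so it could show how many shortfalls come from sampling alone. That works only if shortfalls are counted by arm among everyone who rinsed.

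**Working it through.** **1. The plan's own figure.** The saliva-loss rate is used only in the enrolment number (sections 2.2, 9.1 and 9.2): 43 evaluable per arm, 14% without virus, 10% with insufficient saliva, 55 enrolled.
- Sequential losses: 43 / (0.86 × 0.90) = 55.6.
- Additive losses: 43 / (1 − 0.24) = 56.6, rounded up to 57.

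The stated 55 is reproduced to within 2. No section splits the 10% by arm, or into before and after the rinse.

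**2. Flow needed before and after the rinse** (sections 3 and 5.1).
- Baseline: 5 mL / 5 min = 1.0 mL/min.
- Each post-rinse sample: 2 mL / 5 min = 0.4 mL/min.
- Smallest fall that turns a baseline pass into a post-rinse failure: 1 − 0.4/1.0 = 60%.

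This assumes that the 5-minute limits are enforced. The removal rule is worded by volume, and the précis and sections 6.2 and 6.2.5 give the volumes without a time limit. A participant allowed longer for the baseline sample could have started below 1.0 mL/min.

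**3. What happens to a failure at each time.**

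| Time of failure | Had given 5 mL? | Rinsed? | Survey scheduled before this sample? | Handling |
|---|---|---|---|---|
| Baseline | No | No | No | Removed, replaced |
| 0 min | Yes | Yes | No | Removed, replaced |
| 15 or 30 min | Yes | Yes | Yes | Removed, replaced |
| 45 or 60 min | Yes | Yes | Yes | Kept, shortfall logged |

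The second column follows sections 3, 5.1, 6.2.5 and 8. Two other places disagree: section 5.4 puts the baseline sample after the rinse, and section 10.3.3 leaves baseline out of its removal rule.

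**4. How many people this could be.** If the whole 10% failed after the rinse (an assumption, and the upper end of the planned allowance), that is 0.10 × 84 = 8.4 per arm, or about 25 of 252. At the other stated arm size it is 0.10 × 55 = 5.5. If removals are replaced until 84 complete, 84/0.90 = 93.3 are randomised per arm and about 9 are removed. Should a rinse raise the rate (assumed range):

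| Rate on that rinse | Removed before reaching 84 completers | Power to detect against 10%, 84 per arm, two-sided 0.05 |
|---|---|---|
| 15% | 84/0.85 − 84 ≈ 15 | 0.16 |
| 20% | 84/0.80 − 84 = 21 | 0.44 |
| 25% | 84/0.75 − 84 = 28 | 0.73 |
| 30% | 84/0.70 − 84 = 36 | 0.91 |

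A by-arm table would thus detect a large drying effect but not a small one, so the result should be given as a difference with its interval.

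**5. How firm an illustration is.** With assumed counts of 4/84 on water and 13/84 on one rinse, the difference is 10.7 points (Wald 95% CI 1.7 to 19.7; Fisher p = 0.038). With 12 events instead of 13, p = 0.063. At 55 per arm, 3 v 8 gives 9.1 points (CI −2.0 to 20.2; p = 0.20). These counts show scale only; the documents give no evidence that any rinse dries the mouth.

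**The case against.** A reader might infer that a drying effect can never reach the adverse-event or tolerability result. The documents do not support that:
- Section 7.3 covers any new or worsened finding regardless of cause, and nothing stops staff recording an adverse event as well as a removal.
- Section 10.3.3 logs each shortfall in cause-neutral terms, so counts by arm can be recovered.
- Failures at 45 and 60 minutes stay in the study.
- On the section 3 schedule, those failing at 15 or 30 minutes have already been surveyed, and no section says their answers are discarded.

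Nor is the xerostomia sentence a coding rule. It speaks of some individuals and covers baseline failures, where it is reasonable.

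A reader might also infer that a post-rinse failure shows a rinse effect. It does not. Giving 5 mL and then several further samples could deplete saliva on water too, and the 60% fall depends on the time limits being kept.

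Finally, a reader might want every shortfall declared an adverse event. Missing a collection volume is not plainly an unfavourable sign under section 7.3. Section 7.5 would then send each such person to hospital with a call a week later, and sections 7.3 and 7.4 require a report to the ethics board within 30 days.

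All of this stands, and it reduces the point to one of handling and reporting. It does not remove it. The only reason offered for low flow is a pre-existing one, the removal follows exposure, and no summary by arm is planned. The survey does not fill the gap: no dryness item is named, and it is scheduled before the 15-minute sample.

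**Conclusion.** The concern holds in a limited form. For failures at 0, 15 and 30 minutes after the rinse, the plan applies a removal rule after randomisation and exposure, and the explanation it offers fits its own sample volumes poorly. The data are logged, but no section reports these removals by arm or says that removed participants stay in the safety and survey results. A drying effect of a rinse could therefore go unreported.

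The size is unknown. The planned allowance implies at most about 8 of 84 per arm if all of it falls after the rinse; the true split is not given. The argument rests on the baseline sample coming before the rinse, as in sections 3, 5.1, 6.2.5 and 8, and, for the 60% figure, on enforcement of the 5-minute limits. It claims neither that a rinse dries the mouth nor that adverse-event recording is blocked.

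**What to change.** 1. In sections 6.2.5, 8 and 10.3.3, confine the unrecognised-xerostomia explanation to failure at the baseline sample.
2. State that every participant who rinsed stays in the safety and tolerability denominators, including any survey answers given before removal.
3. Add one table from the CDART data: number and percentage with insufficient saliva at each post-rinse time, and number removed, by rinse. Use all who rinsed as the denominator, and give the difference from sterile water with its 95% CI.
4. Do not make every shortfall an adverse event automatically. Reconcile sections 6.2.5, 8 and 10.3.3 with the definition in 7.3 and the follow-up in 7.5, so that staff know when a shortfall is to be recorded as one.
5. Reconcile sections 5.4 and 10.3.3 with sections 3 and 6.2.5 on when the baseline sample is taken and whether failing it leads to removal.

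The cost is one extra table and minor wording changes. The volumes and withdrawals are already recorded, so no new data collection is needed.

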7. SAFETY ASSESSMENTS

The following table lists possible adverse effects associated with each mouth rinse proposed in this study:

mouth rinse*	Adverse effects
26.9% ethanol plus essential oils	
• If more than used for rinsing (20ml) is accidentally swallowed, get medical help or contact a Poison Control Center right away. The exact amount used for rinsing (20ml) will be dispensed to study participants, such that they cannot swallow more than 20ml, to reduce the risk of this adverse event.• Poison control: [contact]

0.1% Cetylpyridinium Chloride	
 • If more than used for rinsing (20ml) is accidentally swallowed, get medical help or contact a Poison Control Center right away. The exact amount used for rinsing (20ml) will be dispensed to study participants, such that they cannot swallow more than 20ml, to reduce the risk of this adverse event. • Poison control: [contact]
Sterile Water	No contraindications

**All mouth rinses are commercially available in the USA, routinely used in clinical settings, and will be used in an on-label manner.*

The use of on-label, widely used mouth rinses (like Listerine) and collection of saliva carry minimal risk for participants, apart from the very rare, undiagnosed allergy, and the unlikely event that the sample is swallowed. If the case of allergy, UNC Hospital emergency services will be contacted. In the case of swallowing, a Poison Control Center will be contacted.

7.1 Specification of Safety Parameters

Mouth rinse and saliva collection carries low risk and minimal to no safety concerns to the participants. Results of analysis from known COVID+ patients will not require any medical follow-up or safety concerns. As a result, the investigator will monitor subject data, without a safety monitoring board. The investigator and team will meet weekly to review safety concerns, unanticipated problems or adverse events.

7.2 Methods and Timing for Assessing, Recording, and Analyzing Safety Parameters

The investigators and study coordinators will meet weekly to review unanticipated problems with recruitment or adverse events. There is only one site for this study. The use of on-label, widely used mouth rinses (like Listerine) and collection of saliva carry minimal risk for participants, apart from the very rare, undiagnosed allergy, which would be managed through proper referral to the neighboring UNC hospital.

7.3 Adverse Events and Serious Adverse Events

An **adverse event (AE)** is generally defined as any unfavorable and unintended diagnosis, symptom, sign (including an abnormal laboratory finding), syndrome or disease which either occurs during the study, having been absent at baseline, or if present at baseline, appears to worsen. Adverse events are to be recorded regardless of their relationship to the study intervention.

A serious adverse event (SAE) is generally defined as any untoward medical occurrence that results in death, is life threatening, requires inpatient hospitalization or prolongation of existing hospitalization, results in persistent or significant disability/incapacity, or is a congenital anomaly.

The use of on-label, widely used mouth rinses (like Listerine) and collection of saliva carry minimal risk for participants, apart from the very rare, undiagnosed allergy, or the unlikely event that a participant slips or falls during the study, which would be managed through proper referral to the neighboring UNC hospital.

The investigator and team will meet weekly to review safety concerns, unanticipated problems or adverse events. All adverse events will be reported to the IRB and the committee overseeing the study within 30 days.

